6.1. Screening Period

Screening evaluations will be performed for all subjects to determine study eligibility. These evaluations must be completed within 28 days (4 weeks) prior to receiving the first dose of IP unless noted otherwise below. Waivers to the protocol will not be granted during the conduct of this study, under any circumstances.

Screening procedures, as specified in the Table of Events detailed in Section 5, Table 3, will be performed for all subjects to determine study eligibility. All screening procedures must be completed within 4 weeks prior to receiving the first dose of IP.

The electronic patient-reported outcome (ePRO) instrument on a handheld device will be distributed to subjects at the Screening Visit. After completion of a training module, the Pruritus NRS will be completed by the subject daily for at least the last week (7 days) during the Screening Period (prior to Day 1); however, value to assess inclusion criteria will be assessed on Day 1 (Baseline/pre-dose).

Safety laboratory analyses and all assessments will be performed. Screening laboratory values must demonstrate subject eligibility; however, analytes may be repeated (and analysed by the central laboratory) within the screening window, if necessary.

Written, signed, and dated informed consent from the subject prior to the performance of any study related procedures must be obtained by the Principal Investigator or designee (refer to Section 12.3 for further details regarding obtaining subjects informed consent). A copy of the signed informed consent must be given to the subject for his/her records.

The following evaluations will be performed at screening as specified in the Table of Events, after informed consent/assent has been obtained:

- Assessment of inclusion/exclusion criteria
- Demographics and baseline characteristics
- Medical history including atopy status (documentation of AD history, other atopic conditions, and past pharmacotherapy for AD, and other atopic conditions) and as well as details of any prior therapy or procedures to treat AD or other atopic conditions.

- Prior therapy and concomitant therapy (including all procedures occurring ≤ 28 days before screening).
- Adverse event assessment begins when the subject signs the informed consent/assent form. Throughout the course of the study, every effort must be made to remain alert to possible AEs or serious AEs (SAEs). Once subjects consent, AEs/SAEs will be recorded at each study visit. Refer to Section 10 for definitions of AEs/SAEs, monitoring, and reporting
- Hematology, chemistry, coagulation panel, and urinalysis (central laboratory). The following safety laboratory tests will be performed to assess the safety profile of CC-93538:
 - Hematology: red blood cell (RBC) count, total and differential white blood cell (WBC) count (basophils, eosinophils, lymphocytes, monocytes, and neutrophils), platelet count, hemoglobin (hgb), hematocrit (hct), mean corpuscular volume (MCV), mean corpuscular hemoglobin (MCH) and mean corpuscular hemoglobin concentration (MCHC)
 - Blood chemistry: indices included at all required chemistry timepoints are sodium, potassium, chloride, calcium, magnesium, phosphate, blood urea nitrogen, glucose (random, at timepoints not requiring fasting), albumin, alkaline phosphatase, creatinine, creatine phosphokinase (CPK), ALT/SGPT, AST/SGOT, gamma glutamyltransferase (GGT), amylase, total bilirubin, direct bilirubin and C reactive protein (CRP); in addition, fasting lipid panel (total cholesterol, triglycerides, high-density lipoprotein, and low-density lipoprotein) and fasting glucose (instead of random glucose) will be performed only at Day 1 and Week 16/EOT/ET.
 - Coagulation: Prothrombin time (PT), activated partial thromboplastin time (aPTT), and international normalized ratio (INR)
 - Urinalysis: leukocytes, specific gravity, bilirubin, blood, glucose, ketones, pH, protein, and urobilinogen
- Testing for hepatitis B virus (HBV), hepatitis C virus (HCV), and HIV (central laboratory) will be performed at screening only.
 - HBV: Hepatitis B surface antigen (HBsAg) screening test and hepatitis B core antibody (HBcAb) test will be performed. Subjects who test positive for HBsAg will be excluded from the study. For subjects who test positive only for HBcAb, an HBV deoxyribonucleic acid (DNA) test must be performed. If the HBV DNA test is positive, the subject will be excluded from the study. If the HBV DNA test is negative (without antiviral therapy) and ALT and AST are ≤ ULN, the subject will be eligible for this study.
 - HCV: HCV antibody (anti-HCV IgG) test will be performed. Subjects testing
 positive for HCV antibody and have a positive confirmatory test (HCV
 ribonucleic acid [RNA]) will be excluded from the study. Subjects with evidence
 of cleared HCV infection (eg, HCV antibody positive subjects who are negative

for HCV RNA) and who have not received anti-HCV therapy for at least 12 weeks will be eligible for participation.

- HIV: An HIV antibody test will be performed. Subjects testing positive for HIV (enzyme-linked immunosorbent assay [ELISA] test result, confirmed by western blot) will be excluded from the study.
- Testing for tuberculosis (TB) will be performed at screening only. Active TB must be ruled out according to local medical practices. TB must be assessed with a TB skin test, QuantiFERON Gold test, or other interferon gamma release assay (IGRA) (eg, T-SPOT). Subjects with latent TB must have documentation of completed prophylactic treatment by local standard of care. Subjects with an indeterminate test result using any IGRA test, must be discussed for eligibility on a case by case basis by the Sponsor's Medical Monitor or designee. Subjects with latent TB who were only partially treated or who are currently receiving prophylactic treatment will not be eligible for randomization.
- Serum pregnancy test (only for FCBP). A test for the β-subunit of serum human chorionic gonadotropin (β-hCG) must be performed at screening in females of childbearing potential. Urine (or serum) β-hCG will be performed at Day 1 and at the timepoints outlined in the Table of Events (Table 4). In the event of a positive urine test, the subject is not to be dosed, and confirmation with a serum pregnancy test should be performed. At screening and at each subsequent study visit, the Investigator will counsel FCBP subjects on pregnancy precautions for the duration of the study.
- Physical examination: A complete physical examination (including evaluation of heart, lung, head and neck, abdomen, neurological assessment, and extremities) will be performed.
- Height and weight.
- Vital signs: Heart rate, blood pressure (systolic and diastolic), respiratory rate, and temperature will be assessed. Blood pressure and pulse will be assessed in a sitting position and once the subject is at rest. An automated validated device may be used, if available.
- Electrocardiogram (ECG): Single 12-lead ECG will be conducted only at the Screening Visit when the subject is at rest and may be repeated to confirm any abnormal findings.
- AD disease activity assessments:
 - vIGA-AD
 - EASI
 - BSA
 - Pruritus NRS

6.1.1. Additional Information Regarding Safety Laboratory Assessments

Analysis of samples will be conducted by a central laboratory. Details regarding collection of samples, shipment of samples, reporting of results, laboratory reference ranges, and alerting abnormal values will be supplied to the site before site initiation in a Study Laboratory Manual. The results of the analysis will be made available to each site by the central laboratory.

Additional and repeat laboratory safety testing may be performed locally at the discretion of the Investigator. As local laboratory data will not be collected in the electronic case report form (eCRF), if feasible, a sample should also be sent to the central laboratory. In addition, when safety laboratory samples are being collected to further assess AEs, it is recommended that serum samples to assess ADA and PK also be collected and sent to the central laboratory, when feasible. Laboratory samples required to confirm study eligibility (eg, liver function test, serology panel, etc) are required to be performed by the central laboratory if a retest is required during Screening. Retesting of specific laboratory parameters to confirm eligibility is allowed once during screening. If upon retest the subject still does not meet eligibility criteria, the subject should be screen failed.

Investigators will be asked to comment on those abnormalities on the respective laboratory result page, including a notation of the clinical significance of each abnormal finding in the subject's source documents. The laboratory reports/records will be filed with the subject's source documents. Reporting of laboratory AEs is described in Section 10.3.

6.1.2. Screening Failures and Rescreening of Potential Subjects

A screen failure is defined as a subject who has given informed consent/assent and failed to meet the inclusion and/or exclusion criteria. Subjects who initially fail to meet the inclusion/exclusion criteria may be re-screened as per the assessment of the Investigator. Subjects who are rescreened will be required to be re-consented and have all required Screening Visit procedures performed. Subjects may be re-screened only 1 additional time for the study without prior consultation with the Medical Monitor.

6.1.3. Rescreening of subjects who develop COVID-19 during the Screening Period

Molecular testing for asymptomatic COVID-19 infection is not required in this study. However, where local requirements or institutional practice are more restrictive, asymptomatic COVID-19 screening may be performed locally, to ensure compliance with current local guidance. In addition, some subjects may develop suspected or confirmed symptomatic COVID-19 infection, or it is discovered that subjects have asymptomatic COVID-19 infection during the Screening Period. In such cases, subjects may be considered eligible for the study after meeting all Inclusion/Exclusion Criteria related to active infection, and after meeting the following criteria:

- At least 10 days (20 days for severe/critical illness) have passed since symptoms first appeared or positive test result, and
- At least 24 hours have passed since last fever without the use of fever-reducing medications, and
- Symptoms (eg, cough and shortness of breath) have resolved, and

- In the opinion of the Investigator, there are no COVID-19 sequelae that may place the subject at a higher risk of receiving investigational treatment, and
- Negative follow-up molecular test for COVID-19 based on institutional, local and/or regional guidelines and/or requirements

6.2. Treatment Period

On Day 1, prior to randomization in the, the baseline assessments (including laboratory assessments, and the optional skin biopsy), as shown in the Table of Events Section 5, Table 4, will be completed prior to the administration of IP. The Investigator will review all available information to confirm subject eligibility.

- Screening laboratory tests will be used to determine eligibility for randomization with the exception of pregnancy tests, which will need to be confirmed by the Day 1 test results.
- A urine (or serum) pregnancy test must be performed for all females of childbearing potential on Day 1 and the results reviewed prior to randomization. A negative pregnancy test result must be obtained prior to randomization. If the urine pregnancy test result is positive but this is believed to be a false positive, the site must perform a serum pregnancy test at the local laboratory to confirm pregnancy status.
- Baseline laboratory tests will be performed on Day 1 for comparison with follow-up tests. However, the results of these tests will not be available prior to randomization on Day 1.
- The baseline vIGA-AD, EASI, BSA, and the subject reported Pruritus NRS performed on 1 Day will be used to assess subject eligibility; the stratification data point for vIGA-AD score will be provided for randomization.

After eligibility has been confirmed and baseline assessments have been completed, eligible subjects will be randomized to treatment on Day 1. Subsequent visits, assessments and procedures will be performed as per the Table of Events Section 5.

- Assessment of inclusion/exclusion criteria to confirm eligibility (Day 1 only)
- Concomitant therapy
- Assessment of AEs/SAEs. In addition, starting at Day 1, device (ie, pre-filled syringe) failures or malfunctions should be captured, and device related AEs should also be collected.
- Hematology, chemistry, fasting lipid panel, and urinalysis
- Urine (or serum) pregnancy test (only for FCBP)
- Physical examination (A complete physical examination (including evaluation of heart, lung, head and neck, abdomen, neurological assessment, and extremities) or an abbreviated (interim/brief) physical examination (including areas with previously noted abnormalities and/or that are associated with any new complaints from the subject) will be performed according to the Table of Events Section 5, Table 4

- Weight
- Vital signs
- Serum antibodies to CC-93538
- Serum CC-93538 PK assessment
- Whole blood and serum biomarkers assessment
- SARS-CoV-2 serology assessment
- Pharmacogenetic assessment, if applicable per government and local regulations, will be collected one time at Day 1 (note, the sample may be obtained at any subsequent visit).
- Optional Skin Biopsy
- AD disease activity and efficacy assessments:
 - vIGA-AD
 - EASI
 - BSA
 - SCORing Atopic Dermatitis (SCORAD) Index
 - Pruritus NRS
 - PROMIS Sleep Disturbance SF
 - Patient Oriented Eczema Measure (POEM)
 - Dermatology Life Quality Index (DLQI)
 - Hospital Anxiety and Depression Scale (HADS)
- IP administration

Refer to Section 6.5 for a detailed description of the efficacy assessments and outcome measures conducted throughout the study.

6.2.1. End of Treatment or Early Termination

For subjects who complete treatment phase of the study (Week 16) or discontinue the study prematurely for any reason (ie, subjects that do not complete Week 16) an EOT/ET visit will be conducted. For subjects who discontinue the study prematurely, every attempt should be made to complete the assessments detailed in the ET Visit conducted as close as possible to the time of study discontinuation. If study discontinuation occurs at the regularly scheduled visit, the ET Visit and all corresponding ET Visit procedures should be conducted. In addition, these subjects should return for the Follow-up Visits.

The evaluations that will be performed at the EOT/ET Visit are specified in Table of Events in Section 5.

6.3. Follow-up Period

6.3.1. Safety Follow-up (Initial [Week 24] and Final [Week 32])

All subjects will be followed for 16 weeks after the EOT/ET visit for AE reporting, as well as SAEs made known to the Investigator at any time thereafter that are suspected of being related to IP, as described in Section 10.1. Subjects will return for an Initial (Week 24) and a Final (Week 32) Follow-up Visit at 8 and 16 weeks, respectively after completion of the EOT/ET Visit. For subjects who prematurely discontinue from the study, the 16 Week Follow Up Period should be based off of the date of last study visit conducted during the Treatment Phase of the study (eg, the ET visit) and therefore, may be conducted earlier then Week 24 and Week 32.

The evaluations that will be performed at the Follow Up Visits are specified in Table of Events Section 5, Table 5.

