9.3. Sample Size and Power Considerations

Approximately 200 subjects will be randomized in this Phase 2 dose ranging study. Randomization will be equal among the 4 dose groups of placebo, mg Q2W, mg Q2W, and mg QW (approximately 50 subjects per group). Assuming a 10% dropout rate, a sample size of 45 subjects per group will provide approximately 90% power to detect a treatment difference relative to placebo (difference in means) of 35% with respect to the primary endpoint of percentage change from baseline in EASI scores at Week 16. In these power calculations superiority over placebo for a particular dose group is met if the lower bound of the (2-sided) 95% confidence interval (z-score) for the treatment difference exceeds zero (adjusted for multiplicity).

The sample size calculations are based on the following considerations for comparing mean percentage changes from baseline in EASI scores at Week 16 versus placebo. In particular, the recent Phase 2b study of dupilumab reported an observed mean for placebo of 18.1% and corresponding treatment differences of 50.1% (standard error [SE = 6.7%]) and 55.7% (SE = 6.7%), for the doses of 300 mg Q2W, and 300 mg QW, respectively (Thaci, 2016). This study evaluating CC-93538 is designed to detect a (true) treatment difference relative to placebo of 35%. We assume a (true) mean of 20% for placebo, and means for the active dose groups corresponding to treatment differences of 25% mg Q2W), 30% mg O2W), and 35%mg QW), with a common standard deviation (SD) of 50%. We note that the common SD assumption of 50% for the percentage change from baseline in EASI scores at Week 16 was also assumed in the dupilumab Phase 2b study design (Thaci, 2016). Under these assumptions, it is estimated that with a sample size of 45 subjects per group the study provides approximately 90% power to detect superiority relative to placebo for at least 1 dose at the overall type-1 error of α = 0.05 (two-sided) using a hierarchical testing approach (in the order of mg QW versus placebo. mg Q2W versus placebo, and mg Q2W versus placebo).

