9.7. Safety Analysis

All analyses of safety data will be conducted using the Safety population by treatment for the entire study duration of 32 weeks. The assessment of safety will include AEs, SAEs, AEs leading to discontinuation of study treatment, and AEs leading to discontinuation from the study; changes from baseline in laboratory values and vital signs; and incidence and type of laboratory, vital signs, and physical examination abnormalities. Individual data listings will also be provided.

Adverse events will be monitored during the trial, and the data will be summarized by worst severity grade. Adverse events, with focus on treatment-emergent AEs, will be summarized by Medical Dictionary for Regulatory Activities (MedDRA) system organ class, and preferred term. Investigational product-related AEs, AEs leading to death or to discontinuation from treatment, events assessed as moderate or severe, IP-related events, and SAEs, and events of interest.

Laboratory assessments will be performed by a central laboratory. All summaries will be based on the Standard International System of Units (SI) provided by the central lab. Each subject's hematology, blood chemistry, and urinalysis values will be flagged as "low", "normal", or "high" relative to the normal ranges of the central laboratory.

Summary statistics of actual values and changes from baseline in vital signs will be provided by visit.

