10. ADVERSE EVENTS

10.1. Monitoring, Recording and Reporting of Adverse Events

An AE is any noxious, unintended, or untoward medical occurrence that may appear or worsen in a subject during the course of a study. It may be a new intercurrent illness, a worsening concomitant illness, an injury, or any concomitant impairment of the subject's health, including laboratory test values (as specified by the criteria in Section 10.3), regardless of etiology. Any worsening (ie, any clinically significant adverse change in the frequency or intensity of a preexisting condition) should be considered an AE. A diagnosis or syndrome should be recorded on the AE page of the CRF rather than the individual signs or symptoms of the diagnosis or syndrome.

Abuse, withdrawal, sensitivity or toxicity to an investigational product should be reported as an AE. Overdose, accidental or intentional, whether or not it is associated with an AE should be reported on the overdose CRF. (See Section 7.2.3 for the definition of overdose). Any sequela of an accidental or intentional overdose of an investigational product which meets the definition of an adverse event, should be reported as an AE on the CRF. If the sequela of an overdose meets serious criteria, then it must be marked as serious on the CRF. The overdose itself should not be reported as an AE.

In the event of overdose, the subject should be monitored as appropriate and should receive supportive measures as necessary. There is no known specific antidote for CC-93538 overdose. Actual treatment should depend on the severity of the clinical situation and the judgment and experience of the treating physician.

All subjects will be monitored for AEs during the study. Assessments may include monitoring of any or all of the following parameters: the subject's clinical symptoms, laboratory, pathological, radiological or surgical findings, physical examination findings, or findings from other tests and/or procedures.

All AEs will be recorded by the Investigator from the time the subject signs informed consent until 16 weeks after the last dose of IP, or the last Follow Up visit, whichever is longer, as well as those SAEs made known to the Investigator at any time thereafter that are suspected of being related to IP. All AEs (serious/non-serious) will be recorded on the CRF and in the subject's source documents. Refer to Section 10.5 for instructions on how to report SAEs to Drug Safety.

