11. DISCONTINUATIONS

11.1. Treatment Discontinuation

The following events are considered sufficient reasons for permanently discontinuing a subject from the IP:

- Adverse event
- Physician decision
- Lack of efficacy
- Protocol deviation
- Withdrawal by subject
- Death
- Lost to follow-up
- Non-compliance with IP
- Other (to be specified on the eCRF)

Subjects who are permanently discontinued from IP will be encouraged to continue participation in the study without IP administration in order to complete all remaining required study assessments including efficacy evaluations. Subjects who decline further participation in the study should complete the early termination visit, and follow up visit assessments. Subjects who discontinue early from IP and/or study participation will not be replaced.

The reason for discontinuation of treatment should be recorded in the CRF and in the source documents.

The decision to discontinue a subject from treatment remains the responsibility of the treating physician, which will not be delayed or refused by the Sponsor. However, prior to discontinuing a subject, the Investigator may contact the Medical Monitor and forward appropriate supporting documents for review and discussion.

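### Section 9.7 summarises adverse events over one 32-week duration with no measure of time at risk, although study leavers are observed for less; unequal withdrawal can bias dose-versus-placebo safety percentages

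*Combined protocol and SAP*

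**What the plan says.** Protocol Section 6.3.1 sets the general rule: "All subjects will be followed for 16 weeks after the EOT/ET visit for AE reporting". For those who leave the study prematurely, "the 16 Week Follow Up Period should be based off of the date of last study visit conducted during the Treatment Phase", so their two follow-up visits "may be conducted earlier then Week 24 and Week 32". Section 10.1 gives a matching recording window for adverse events, running from consent "until 16 weeks after the last dose of IP, or the last Follow Up visit, whichever is longer".

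Section 9.7 then states: "All analyses of safety data will be conducted using the Safety population by treatment for the entire study duration of 32 weeks". On adverse events it says that "the data will be summarized by worst severity grade" and that they will be tabulated by system organ class and preferred term. It names no subject-time rate, no censoring rule and no time-to-event method. Section 9.2 puts every subject with at least one dose in the Safety population. Table 2 describes the safety endpoint as incidence, with a timeframe running through the Final Follow Up Visit.

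Stopping investigational product (IP) is kept separate from leaving the study. Section 11.1 says: "Subjects who are permanently discontinued from IP will be encouraged to continue participation in the study without IP administration". Sections 7.2.6 and 8.4 say the same for the cases they cover.

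**The concern.** A crude percentage divides subjects with an event by all dosed subjects, whatever time each was observed. A subject who withdraws at Week 4 and has no event by Week 20 adds one to the denominator, exactly like a subject observed without an event for 32 weeks. An arm that loses more subjects has less time in which events can be seen, so its percentage is pulled down.

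More withdrawal on placebo would make the doses look less safe against placebo than they are. More withdrawal on an active arm would flatter that dose. Comparing the safety and tolerability of three regimens with placebo is a stated secondary objective, and Section 6.6 describes this as the first study of the drug at higher cumulative exposures. Reporting on-treatment and follow-up periods separately would not by itself remove the problem, because observation time could still differ between arms within each period.

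**Working it through.** **The plan's own figures.** The documents give no figure for adverse-event incidence or time at risk. The one relevant input is in Section 9.3: "Assuming a 10% dropout rate", 45 subjects per group remain. That reproduces: 45 / (1 − 0.10) = 50 per arm. The rate is not split by arm.

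**Observation time lost.** A completer is observed for 16 + 16 = 32 weeks. A subject who leaves the study at Week w and attends follow-up is observed for w + 16 weeks, losing (16 − w)/32 of the period:
- Week 1: 15/32 = 47%
- Week 4: 12/32 = 37.5%
- Week 8: 8/32 = 25%
- Week 15: 1/32 = 3%

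A subject who never returns is observed for w weeks only.

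**Assumptions, none from the documents.** The true 32-week incidence is p = 0.40 in both arms. The hazard is constant. Leaving times are spread evenly over Weeks 1 to 15. Dropout means leaving the study, and it differs by arm as shown below.

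**Formulas.**
- Hazard: h = −ln(1 − 0.40)/32 = 0.01596 per week.
- Mean event probability for leavers who attend follow-up: average of 1 − exp(−h(w + 16)) over w = 1 to 15, which is 31.66%.
- Mean event probability for leavers who never return: average of 1 − exp(−hw), which is 11.78%.
- Crude incidence with dropout d: 40% − d × (40% − leaver mean). The shortfall per leaver is 8.34 points (attend) or 28.22 points (none return).
- False excess, active minus placebo: (placebo dropout − active dropout) × shortfall.

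**Results.**

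| Dropout, placebo vs active | Leavers | Crude incidence, placebo vs active | False excess |
|---|---|---|---|
| 20% vs 7% | all attend | 38.3% vs 39.4% | 0.13 × 8.34 = 1.1 points |
| 20% vs 7% | none return | 34.4% vs 38.0% | 0.13 × 28.22 = 3.7 points |
| 30% vs 8% | all attend | 37.5% vs 39.3% | 0.22 × 8.34 = 1.8 points |
| 30% vs 8% | none return | 31.5% vs 37.7% | 0.22 × 28.22 = 6.2 points |
| 10% vs 10% | all attend / none return | both arms 0.8 / 2.8 points low | 0 |

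If the active arm loses more subjects, the sign reverses.

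**Sensitivity.** These runs take leaving as uniform over Weeks 0 to 16 and true incidences of 10%, 30% and 60%. At 20% vs 10% dropout the false excess is 0.24, 0.66 and 1.07 points if leavers attend, and 0.74, 2.16 and 4.02 if none return. At 30% vs 10% it is 0.48, 1.33 and 2.15, or 1.48, 4.32 and 8.04.

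**Scale.** With 50 per arm and 40% incidence, the standard error of a difference is sqrt(2 × 0.4 × 0.6 / 50) = 9.8 points. In this model the rates per subject-time at risk are equal in the two arms, so the artefact vanishes on that basis.

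**The case against.** The strongest reply is that the plan already limits the problem. Lack of efficacy and systemic rescue are grounds for stopping IP, not entries in the Section 11.2 list of reasons for leaving the study. Subjects who stop IP are encouraged to stay, and those who do keep the full 32 weeks. That stands: only study withdrawals lose observation time. Retention is encouraged, not guaranteed, and Section 8.4 foresees subjects who decline. Withdrawal by subject and loss to follow-up are listed in Section 11.2.

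Second, Sections 6.2.1, 6.3.1 and 7.2.6 expect leavers to attend both follow-up visits. That also stands, so the 1-to-2-point figures describe the plan as written. The 4-to-6-point figures are a bound for the case where nobody returns.

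Third, Section 9.7 is descriptive, with no test or interval against placebo, and Section 9.5 reports discontinuation by arm. An imbalance in numbers would be visible. Counts and reasons do not give time at risk, however, and the objective is still a comparison.

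Fourth, Section 9.1 defers unstated detail to the SAP, and the material contains no separate SAP text. The point may be settled there. The deferral is general, though. Section 9.6.2.1 expressly leaves the censoring rules of the pruritus endpoint to the SAP, while Section 9.7 has no such pointer.

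A reader might infer that placebo will lose more subjects and that the safety comparison is therefore distorted against the drug. The documents do not support this. They give 10% dropout without a split by arm, and the IP-stopping rules do not predict who leaves the study. A reader might also infer that the plan declares leavers event-free to Week 32. It does not say so; this is what a crude percentage does by default.

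**Conclusion.** The point holds as a gap in the safety analysis with a possible bias, not as a demonstrated distortion. Study leavers are observed for less than 32 weeks, and Section 9.7 does not say how that is handled. Under the assumed splits the bias is about 1 to 2 points if leavers attend follow-up and about 4 to 6 points if none do. With equal withdrawal the difference is unbiased, although both percentages are low. Either direction is possible.

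The 20% vs 7% split, with 7% in all three active arms, averages (20 + 3 × 7)/4 = 10.25%, close to the planned rate. The 30% vs 8% split averages (30 + 3 × 8)/4 = 13.5% and is above it. With follow-up attended, the bias is roughly one-ninth to one-fifth of the 9.8-point standard error (1.1/9.8 and 1.8/9.8). It is systematic, however, and the remedy is cheap. The sizes rest on the assumed incidence, constant hazard, leaving times and dropout by arm.

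**What to change.** In Section 9.7, or in the SAP with a cross-reference from it, keep the crude percentages and add beside them, for each arm:
- total and median observation time;
- follow-up-adjusted incidence of first event: subjects with an event per 100 subject-years at risk, with time ending at first event or last contact;
- Kaplan-Meier cumulative incidence as support.

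Do this for any treatment-emergent adverse event, serious adverse events, adverse events of special interest and adverse events leading to discontinuation. Settle the wording before the primary analysis database lock, after which Section 3.1 no longer requires the blind to be kept. If the SAP already covers this, a one-line reference in Section 9.7 closes the point.

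The cost is a few extra tables, built from event start dates and contact dates that should already be collected. The follow-up schedule, design and sample size do not change. The added figures have their own assumptions: subject-year rates need a roughly constant hazard, which is doubtful across dosing and washout, and Kaplan-Meier needs withdrawal to be non-informative. They should therefore supplement the crude percentages, not replace them.
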